## 7.2 Exclusion Criteria

1. Prior usage of PD-1 inhibitors, programmed-death ligand 1 and/or 2 inhibitors, CTLA-4 inhibitors including but not limited to ipilimumab, nivolumab, avelumab, durvalumab, tremelimumab, and pembrolizumab.
2. Active on-going immunologic or autoimmune disease including but not limited to systemic or cutaneous lupus erythematosus, cutaneous psoriasis, psoriatic arthritis, rheumatoid arthritis, scleroderma, sicca syndrome, polymyalgia rheumatica, polyarteritis nodosa, granulomatous

- polyangiitis, microscopic polyangiitis, polyarteritis nodosa, temporal arteritis, giant cell arteritis, dermatomyositis, Kawasaki disease.
3. Previous malignancy within 3 years other than non-melanomatous skin cancers or cancers of low malignant potential such as non-invasive urothelial carcinoma.
  4. Any other on-going chemotherapeutic, biologic, radiopharmaceutical, or investigational agent currently or within 28 days of Cycle 1 Day 1.
  5. Prior use of abiraterone and other hormonal agents used to treat prostate cancer are permitted but abiraterone acetate should be stopped prior to study treatment initiation.
  6. Current usage of immunosuppressant medication except for a) intranasal, inhaled, and topical corticosteroids and b) systemic corticosteroids equivalent to  $\leq 10$  mg/day of prednisone, c) steroids as premedication for hypersensitivity reactions (e.g. CT scan premedication).
  7. Prior organ transplantation including allogeneic stem-cell transplants.
  8. Active bacterial or viral infections requiring systemic therapy.
  9. Current active infections with HIV/AIDS, Hepatitis B, and Hepatitis C requiring treatment.
  10. Live virus vaccination within 4 weeks of the first dose of avelumab (inactivated vaccines are allowed).
  11. Known prior hypersensitivity to the investigational product or any component formulations, including known severe hypersensitivity reactions to monoclonal antibodies.
  12. Clinically significant (i.e. active) cardiovascular disease: cerebral vascular accident (<6 months prior to enrollment), myocardial infarction (<6 months prior to enrollment), unstable angina, congestive heart failure ( $\geq$  New York Heart Association Classification Class II), or serious cardiac arrhythmia requiring medication.
  13. Persisting toxicity related to prior therapy (NCI CTCAE v. 4.03 Grade  $> 1$ ); however, alopecia, sensory neuropathy Grade  $\leq 2$ , Grade 2 anemia, or other Grade  $\leq 2$  not constituting a safety risk based on investigator's judgment are acceptable.
  14. Other severe acute or chronic medical conditions including colitis, inflammatory bowel disease, pneumonitis, pulmonary fibrosis or psychiatric conditions including recent (within the past year) or active suicidal ideation or behavior; or laboratory abnormalities that may increase the risk associated with study participation or study treatment administration or may interfere with the interpretation of study results and, in the judgment of the investigator, would make the patient inappropriate for entry into this study.

## 8 SCREENING AND ON-STUDY TESTS AND PROCEDURES

Activity	≤35 Days Prior to Dosing	Cycle Duration = 28 days (+/- 3 day window of allowance) 		Post Treatment (+/- 7 days)		
	Screening / baseline	Day 1 of every cycle 	Day 15 of every cycle 	EOT / Progression/ Withdrawal 	Safety follow up (28 days post treatment)	Long Term Follow-Up (every 3 months)
Baseline Documentation						
Informed Consent	X					
Inclusion/Exclusion Criteria	X					
Central histology review of tumor tissue, Duke pathology	X					
Medical/Oncological History 	X	X	X	X	X	X
Laboratory Studies						
Hematology 	X	X	X	X	X	
Blood Chemistry 	X	X	X	X	X	
Urinalysis 	X					
PSA	X	X		X	X	
Testosterone	X	X		X		
Thyroid Studies 	X	X		X	X	
Tumor Markers 	X	X		X		
Study Treatment						
Study Treatment – ADT +/- enzalutamide (SOC) 	X	X	X	X		
Study Treatment – Avelumab 		X	X			
Tumor Assessments						
Tumor Imaging 	X	X		X		
Post-Progression Biopsy 				X		
Clinical Assessments						
Physical Examination 	X	X	X	X	X	

KPS, Weight, Vitals	X	X	X	X	X	
Adverse Events 		X	X	X	X	
Conmed/Treatment 	X	X	X	X	X	
Survival Follow-up 						X
Research Laboratory Studies (Cycle 1 day 1, Cycle 3 day 1 and EOT)						
Immune cell monitoring 		X		X		
Cell Free DNA 		X		X		
CTCs for culture 		X		X		
Patient Reported Outcomes						
FACT-P 		X		X		

## Footnotes:

- Day 1 Cycle 1 Assessments:** Hematology, blood chemistry, PSA, testosterone, and PSA need **not** be obtained on day 1 if a screening sample has been performed within 14 days. Baseline Signs/symptoms are only needed on Cycle 1 Day 1. Thyroid studies do not need to be repeated on Day 1 of Cycle 1 if obtained within the screening window.
- Cycle 1 Day 15+:** Avelumab can be given up to 3 days before or after the expected start date of each infusion/treatment day after Cycle 1 Day 1. Cycles are continued until progression or until significant adverse event.
- End of Treatment/Progression/Withdrawal: To occur at time of decision to end treatment.** These assessments do **not** need to be completed if they have been performed within 7 days of study withdrawal (within the last 6 weeks for tumor assessments). +/- 7 day window of allowance. Treatment beyond radiologic or PSA progression is permitted if there is potential for clinical benefit with continued therapy. Research blood samples will be collected at iRECIST-defined progression or at the EOT visit, whichever comes first.
- Medical/Oncological History:** Includes oncologic history, demographics, history of other disease processes and concomitant illnesses. Central review of pathology at Duke is required at baseline.
- Samples for hematology, blood chemistry, and thyroid studies:** CBC w/ differential, CMP (including AST, ALT, Alkaline Phosphatase), LDH, phosphorus, TSH, free T4. Thyroid studies must be performed at least every 8 weeks starting after cycle 1 and at end of treatment/safety follow-up (if not performed in the previous 8 weeks). PSA and testosterone should be performed at least every 4 weeks.
- Urinalysis:** Tests will be done at screening, then as clinically indicated thereafter; tests to be performed at the local laboratory. Urinalysis should also include a urine spot protein at baseline. A 24 hour urine analysis is required if urine protein is > 1+.
- Tumor Markers:** CEA and chromogranin A will be measured at baseline and those that are elevated will be measured every 4 weeks thereafter. (Standard of care)
- Standard of Care Treatment (Androgen Deprivation Therapy (ADT), +/- enzalutamide):** Patients already on ADT at study entry should continue with dosing and administration is to be determined by the treating provider but can include gonadotropin releasing hormone

agonists or antagonists. ADT will continue throughout all cycles. If patient has pure SCPC they do not need to be started on ADT but are allowed to continue per treating provider if already on ADT. Concurrent enzalutamide is permitted.

9. **Study Treatment (Avelumab):** Avelumab will be administered at 10 mg/kg IV every 2 weeks. One cycle is 2 infusions (4 weeks).
10. **Tumor imaging:** Bone scan, and either CT or MRI scans of the chest, abdomen, and pelvis will be performed to assess disease status at baseline as well as every 8 weeks or at treatment discontinuation (if imaging did not occur within 6 weeks of visit ) as well as whenever disease progression is suspected, to confirm partial or complete response. NaF-PET/CT may be used in place of bone scan and CT in select cases. In all cases, the same imaging modality should be used throughout the study on individual subjects. Baseline tumor imaging must be performed within 35 days of cycle 1 day 1. MRI brain should be done in all subjects at baseline if indicated clinically and should be followed every 8 weeks with the other scans if metastasis(es) are found or if disease progression is suspected. Allowable window for tumor assessment imaging studies is +/- 7 days. Subjects removed from therapy for any reason other than disease progression will continue to be followed for radiographic progression until additional treatments are started, when available.
11. **Post-Progression Biopsy:** An optional standard of care post-treatment progression biopsy will also be collected and additional tissue for research will be banked in the Biospecimen Repository & Processing Core (BRPC) under Pro00080869 for future research on resistance mechanisms including assessment of immune checkpoint status.
12. **Physical Examination:** Examination of major body systems. It does **not** need to be done cycle 1, day 1 if performed within the last 7 days.
13. **Adverse Events:** Subjects must be followed for adverse events from the first day of study treatment until 28 days after the last dose of study treatment, or until all serious or study drug-related toxicities have resolved or are determined to be “chronic” or “stable”, whichever is earlier. Serious adverse events should be monitored and reported from the time the patient starts study drug treatment as described in the protocol.
14. **Concomitant medications/treatments:** Concomitant medications and treatments will be recorded from up to 35 days prior to the start of study treatment, during the study, and through the safety follow up visit.
15. **Survival Follow up:** After the EOT/Withdrawal of treatment, subjects will be surveyed for their survival status by either a direct phone call or through the chart review. A clinic visit on study is not needed. The subjects will be surveyed every 3 months for up to 3 years, unless the subject has requested otherwise.
16. **Immune Cell Monitoring and Cell Free DNA:** Research blood samples will be collected at 3 time points during the course of therapy. At initiation (Cycle 1 Day 1), on Cycle 3 Day 1, and at progression. A total of four blood tubes will be collected at each interval. Three tubes will be processed for the immune cells. Plasma samples (single EDTA tube) will also be collected and processed at each time point. (see laboratory manual for details on shipping and handling)
17. **CTCs for culture:** Research blood will be collected on cycle 1 day 1 and at progression for circulating tumor cell enrichment and cell culture.
18. **PROs:** Patient reported outcomes will be assessed using the Functional Assessment of Cancer Therapy – Prostate (FACT-P). Subjects will first complete the questionnaire in clinic prior to administration of study medication. Subjects will then be asked to complete a follow up FACT-P on day 1 of cycles 1, 4, 7 and every 3 subsequent cycles, and at End of Treatment/Withdrawal

## 8.1 Screening Examination

The screening examination will take place within 35 days of initiation of therapy. An informed consent form must be signed by the subject before any screening procedure takes place.

Subject data to be collected at the Screening Examination includes:

- Informed consent process utilizing a signed and dated IRB-approved ICF
- Confirmation of inclusion/exclusion criteria
- Medical history including demographics, concomitant illnesses and oncologic history. Oncologic history must include specific documentation of prostate cancer histologic diagnosis.
- Prior and concomitant medications and non-pharmacologic treatments taken within 4 weeks of screening will be recorded. In addition, all prior treatments including surgery and radiotherapy for prostate cancer will be recorded, regardless of when administered.
- Standard of Care tumor imaging within 35 days of Cycle 1, Day 1 must include:
  - CT of the chest, abdomen, and pelvis for tumor assessment And
  - Whole body bone scan (99-Tcnetium), standard-of-care
  - Note: NaF-PET/CT may be used in place of bone scan and CT in select cases
  - MRI Brain should be performed if clinically indicated based on symptoms of CNS metastases
- Sample collection for the following laboratory evaluations (all standard-of-care):
  - Complete blood count (CBC) with differential: WBC count with differential, platelet count, hemoglobin, and hematocrit.
  - Serum chemistries: Sodium, potassium, chloride, blood urea nitrogen (BUN) or urea, creatinine, glucose, carbon dioxide (CO2) or bicarbonate, calcium, total protein, aspartate aminotransferase (AST), alanine aminotransferase (ALT), albumin, total bilirubin, and alkaline phosphatase, thyroid stimulating hormone (TSH), free thyroxine (fT4).
  - Urinalysis
  - Testosterone
  - PSA levels.
  - Tumor markers (CEA and chromogranin A)
- Physical examination to be conducted and height (cm), weight (kg), and vital signs (including temperature [°C], blood pressure [mmHg], heart rate [beats per minute], and respiratory rate [breaths per minute]) to be measured and recorded
- Karnofsky performance status
- Pathology review

## 8.2 Subject Registration and Enrollment

### 8.2.1 Informed Consent

Authorized study personnel should fully explain the scope of the study to each subject before obtaining informed consent. Consent should occur prior to any research procedures and before formal screening procedures. Subjects should be advised of any known risks inherent in the planned

procedures, of any alternative treatment options, of their right to withdraw from the study at any time for any reason, and of their right to privacy.

When obtaining informed consent, study personnel should:

**First:** Confirm that the subject is a potential candidate for study participation.

**Next:** Obtain dated and signed informed consent.

**Finally:** Confirm that the subject is eligible as defined in Section 7.0 (Inclusion/Exclusion Criteria). A record of subjects who fail to meet entry criteria (i.e., screening failures) will be maintained.

Subjects will be entered into the Duke clinical trial subject registry per institutional policy.

### **8.2.2 Registration**

Subject registration at each study site/institution will be conducted according to the institution's established policies and all sites will be overseen by the Duke University Medical Center Genitourinary Oncology Group. Prior to registration, subjects will be asked to sign and date an Institutional Review Board (IRB)-approved consent form. After obtaining informed consent, the consent document and any registration documents will be submitted for review and registration of the subject by the lead site (Duke). All consented subjects will be registered and assigned a unique study ID. A record of subjects who fail to meet entry criteria (i.e., screen failures) will be maintained.

Refer to Subject Registration Instructions in the Coordinator Manual for details.

### **8.2.3 Enrollment**

Subjects will be enrolled only after all pre-treatment screening evaluations are completed and all eligibility criteria are met. Once the subject has been registered and found to meet all eligibility criteria, the subject will be approved for enrollment. Study treatment must not commence until the subject has received his/her identification number and enrollment approval from the lead site.

## **8.3 Run-In Period**

Not applicable

## **8.4 Treatment Period**

Treatment will be administered on an outpatient basis. Avelumab will be given every 2 weeks according to the calendar of events. On study procedures are detailed in the schedule of events including blood tests, imaging, medical history and concomitant medications, toxicity assessments, FACT-P assessments, and correlative biomarkers.

## **8.5 End of Treatment**

In the event of disease progression, unacceptable toxicity, or withdrawal of consent, study treatment is to be stopped and an end-of-treatment visit is to be conducted within 7 days.

The following procedures are to be conducted at the end-of-treatment visit:

- Concomitant medications and non-pharmacologic treatments to be reviewed and recorded.
- Sample collection for the following laboratory evaluations (all standard-of-care):

- CBC: WBC with differential, platelet count, hemoglobin, and hematocrit.
- Chemistries: sodium, potassium, chloride, blood urea nitrogen (BUN) or urea, creatinine, glucose, carbon dioxide (CO2) or bicarbonate, calcium, total protein, aspartate aminotransferase (AST), alanine aminotransferase (ALT), albumin, total bilirubin, and alkaline phosphatase, thyroid stimulating hormone (TSH), free thyroxine (fT4).
- Testosterone
- PSA
- Tumor markers (CEA and chromogranin A)
- Progression biopsy of metastatic site (optional) and research blood samples (see laboratory manual).
- Research blood sample collection will occur at this visit or iRECIST defined progression, whichever comes first
- Tumor imaging as per standard of care practices to document progression
- Physical examination to be conducted, including weight (kg) and vital signs (including temperature [°C], blood pressure [mmHg], heart rate [beats per minute], and respiratory rate [breaths per minute]).
- Karnofsky performance status.
- Functional Assessment of Cancer Therapy – Prostate (FACT-P) will be administered

## 8.6 Follow up period

### 8.6.1 Safety Follow-up visit

The safety follow-up visit is to occur 28 days (+/- 7 days) after the last dose of study agent. Subjects that discontinue treatment due to reasons other than progressive disease will be followed until progression through Standard of Care scans.

### 8.6.2 Extended safety follow-up

Given the potential risk for delayed immune-related toxicities, extended safety follow-up must be performed up to 90 days after the last dose of avelumab administration for all serious or study drug-related toxicities were not resolved or not determined to be “chronic” or “stable” within 28 days after the last dose of avelumab. The extended safety follow-up beyond 28 days after last study drug administration may be performed either via a site visit or via a telephone call with subsequent site visit requested in case any concerns noted during the telephone call.

### 8.6.3 Survival Follow-up Period

Subjects will be followed for disease progression and death for a maximum period of 3 years from the date that the Subjects were enrolled to the protocol. Imaging studies and clinical visits will be performed as per standard-of-care.

## 8.7 End of Study

After progression or withdrawal from treatment, each subject will be followed every 3 months following their end-of-treatment visit for a total of 3 years from study enrollment for survival follow

up. The overall end of study will occur when the last enrolled subject has completed his 3 year follow-up visit or death.

## **8.8 Early Withdrawal of Subjects(s)**

### **8.8.1 Criteria for Early Withdrawal**

Subjects may voluntarily withdraw from the study at any time. The PI may also withdraw a subject from the study at any time based on his/her discretion.

Reasons for PI-initiated withdrawal may include the following:

- Symptomatic disease progression or objective radiologic progression that is not consistent with iRECIST
- Unacceptable toxicity, intercurrent illness, or changes in the patient's condition (at the discretion of the treating physician) — Reason(s) for removal must be clearly documented in the physician progress note
- The patient may withdraw from study treatment at any time for any reason and still be followed per protocol.
- Provider decision that the subject is no longer clinically benefiting from avelumab

### **8.8.2 Follow-up Requirements for Early Withdrawal**

Upon early withdrawal from study treatment, an end of treatment visit should be conducted within 7 days as described above. At withdrawal, all on-going study-related toxicities and SAEs should be followed until resolution, unless in the investigator's opinion, the condition is unlikely to resolve due to the subject's underlying disease. Subjects should be followed up for new AEs for 90 calendar days after the last dose of avelumab. All new AEs possibly related to study treatment occurring during that period should be collected.

### **8.8.3 Replacement of Early Withdrawal(s)**

Patients who consent but do not receive a dose of study drug will be replaced and will not be considered evaluable. Subjects who prematurely withdraw but received a dose of study drug will not be replaced.

## **8.9 Study Assessments and Definitions**

### **8.9.1 Medical History**

At the initial visit, the detailed medical history will include concomitant illnesses and oncologic history. All prior treatments including surgery, chemotherapy, hormonal therapy, and radiotherapy for prostate cancer will be recorded, regardless of when administered. This medical history will be

updated at subsequent visits. Concomitant medications and non-pharmacologic treatments taken will be recorded at each visit.

### 8.9.2 Physical Exam

Physical examination should include: height (cm – screening visit only), weight (kg), physical exam findings, and vital signs. Vital signs include temperature [°C], blood pressure [mmHg], heart rate [beats per minute], and respiratory rate [breaths per minute]. Karnofsky performance status will be assessed and recorded at each visit. All additional elements of the physical exam will be documented per the provider's discretion.

### 8.9.3 Correlative Exploratory Biomarker Studies

**1. To describe the impact of PD-L1 inhibition with avelumab on blood-based biomarker changes over time, including PSA, chromogranin-A, cell free DNA, LDH, and alkaline phosphatase.** For Objective 1, Subjects will have standard of care serum CEA and chromogranin A, LDH, PSA, and alkaline phosphatase drawn per the protocol. Samples will be drawn on Day 1 of every cycle. Cell free tumor DNA from plasma (research) will be collected and analyzed at baseline, cycle 3 day 1, and at progression. Changes in these biomarkers over time will be described using descriptive statistics only without formal testing. Please see the lab manual for associated details. Given that these are standard of care measures for NEPC patients and may be clinically useful in monitoring response to treatment, these are not considered research tests.

**2. To determine if levels of circulating biomarkers secreted by neuroendocrine-like prostate cancers correlate with clinical and radiographic treatment response.** For this objective, baseline and longitudinal levels of the biomarkers described in objective 1 will be associated with radiographic and clinical response to avelumab as well as duration of response, PFS, and survival. These are considered exploratory analyses.

**3. To determine if the presence of different immunohistochemical markers on the pre-treatment biopsy specimens prognosticates clinical and radiographic treatment response.** For Objective 3, all Subjects will have already submitted a sample of tumor tissue for central review at Duke University Department of Pathology. Acceptable tissues include local prostate biopsies, surgical specimens, or metastatic biopsies. Outside slides or recuts of outside tissue is required for histologic review prior to enrollment as part of the screening process. Additional formalin fixed tissue (block, biopsy, or slides) may be kept for biomarker studies specific to this trial. These samples will then be assessed for immune checkpoint biomarker expression (PD-1, PD-L1, CD8, and CTLA4 among others) as well as other expression of other tumor specific proteins (PD-L1, PD-L2, AR, PSA, FOXA2, p53, Rb, Cyclin D1, Chromogranin A, synaptophysin, p38 activity, SNAIL, among others). Associations of pre-treatment biopsies with primary and secondary outcomes will be described in an exploratory fashion.

For subjects that opt-in for the post-progression biopsy, additional tissue will also be collected and banked in the Biospecimen Repository & Processing Core (BRPC) under Pro00080869 for future research to identify resistance mechanisms and immune checkpoint status.

**4. To determine if the level of different circulating immune cells correlate with both progressive addition of immunotherapy as well as clinical and radiographic treatment response or disease progression.** For Objective 4, peripheral blood for immune subset phenotyping will be collected from subjects at baseline (Cycle 1 Day 1), at Cycle 3 Day 1, and at disease progression. These will then be processed by the Duke Substrate Services Core & Research Support (SSCRS) laboratory and analyzed in the Duke Immune Profiling Core Laboratory (DIPC) ([name]) at Duke University. Changes in immune cell phenotypes over time will be described during avelumab therapy, as will associations with clinical/radiographic responses and duration of response, PFS. Please see the lab manual for specific details about tube types, processing, collection and storage.

**5. To determine if levels of cell free DNA correlate with clinical and radiographic treatment response.** For objective 5, peripheral blood and plasma will be drawn to collect cell free DNA for analysis. We will measure and characterize cell free DNA at baseline (Cycle 1 Day 1), at Cycle 3 Day 1, and at disease progression. Cell free DNA will be analyzed using whole exome sequencing. Please see the lab manual for further details of plasma processing and collection/storage.

**6. To isolate prostate neuroendocrine-like CTCs for ex vivo culture and characterization studies.** One 7.5 mL EDTA tube of research blood will be collected on cycle 1 day 1 and at progression for circulating tumor cell enrichment, cell culture and serial passaging ex vivo as cell lines for characterization and long-term studies of prostate cancer biology. Please see the lab manual for further details of collection and processing samples for CTCs.

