# 7 SUBJECT ELIGIBILITY

## 7.1 Inclusion Criteria

1. Neuroendocrine-like prostate cancer, based on histology OR based on clinical presentation as defined by meeting one of the two below criteria. All subjects must submit their primary tumor or metastatic biopsy pathology specimens to the Duke Cancer Institute where they will be centrally reviewed by Duke Pathology ([name]). Central Duke pathologic review is not required for screening but rather for confirmation of histologic subtype. Local pathologic review is sufficient for eligibility determination.
  - a. Criterion 1: Presence of 1 of 3 histologically proven diagnoses: **1)** Primary small cell carcinoma of the prostate, defined by classic histologic features such as small tumor cells with scanty cytoplasm, darkly stained nuclei with homogeneous chromatin pattern. The tumor cells do not form glandular structure but grow as solid sheets with frequent mitotic figures and necrosis; **2)** Intermediate atypical carcinoma of the prostate, which has histologic features distinct from small cell carcinoma or adenocarcinoma. The tumor grows as solid sheets or vague glandular structures. The tumor cells have moderate amounts of cytoplasm and centrally located, round and regular nuclei with fine, granular and homogeneous chromatin. Mitosis and necrosis are absent; **3)** mixed histology tumors of the prostate, containing both adenocarcinoma and neuroendocrine or small cell components.
  - b. Criterion 2: Presence of histologically proven adenocarcinoma of the prostate without any sign of neuroendocrine or small cell histology that is radiographically progressing despite castrate levels of testosterone (<50 ng/mL) with the following poor risk features:
    - i. Prior progression despite therapy with either abiraterone acetate and/or enzalutamide
    - ii. At least one of the following: 1) Liver metastases; 2) Bulky radiographic progression ( $\geq 2$  cm short axis lymph nodes or  $\geq 1$  cm long axis visceral metastases) combined with low serum PSA (<10ng/mL); 3) High serum LDH (>1X upper limit of normal).
2. Measurable disease as defined by modified PCWG3 using iRECIST criteria
3. Available tumor tissue for pathologic review and correlative studies. Tumor tissue (localized or metastatic) does not need to be received but rather identified and available (slides and/or blocks) to be sent to Duke.
4. Documented progressive metastatic CRPC based on at least one of the following criteria:

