### 11.1 Sample Size Estimation

This study will use the optimal two-stage design of Simon to test a hypothesis about response rate in subjects with NEPC treated with avelumab. Response will be defined as a complete (CR) or partial response (PR). Assuming that the response rate among subjects treated is 5%, the trial is designed to have 88% power with a one-sided type I error rate=5% to reject the null hypothesis of response rate of 5% when the true response rate was 20%. In the first stage, 18 subjects will be enrolled and if one or fewer responses are observed the trial will be terminated. However, if two or more responses are observed, an additional 26 subjects will be enrolled at the second stage for a total of 44 subjects. If five or more subjects respond, this new agent would be declared to have promising activity. This design has 88% power to conclude an agent is promising if its true objective response proportion is 20%; Type 1 error rate (one-sided) is 0.05 (this is the probability to conclude that a given agent is promising if its true objective response proportion is 5%). The probability of early termination under the null hypothesis is 0.77. These operating characteristics were selected to represent a reasonable compromise between high power, low false positive rates, and desire for small sample sizes, especially in the first stage. Allowing for 10% unevaluable rate, the target sample size is 49 subjects.

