### 11.5.3 Handling of Missing values, censoring, and discontinuations

Ineligible subjects and subjects who cancel registration before receiving any therapy will not be included in the analyses. We will follow each patient long enough to avoid censoring due to end of study. The binomial test assumes that other censoring than due to end of study is rare. The study results are just important reference and more studies are necessary for medical decision making.

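### The plan disagrees on whether central pathology review precedes entry, and on whether a dosed man later judged ineligible stays in the primary response rate

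*Combined protocol and SAP*

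**What the plan says.** **Entry.** Inclusion criterion 1 (section 7.1, repeated in the synopsis) states "Central Duke pathologic review is not required for screening but rather for confirmation of histologic subtype" and adds that a local read is enough to determine eligibility. Inclusion criterion 3 says that tumour tissue "does not need to be received but rather identified and available".

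Four other places point the other way:
- Section 8.9.3, objective 3, discussing tissue submitted for central review: "Outside slides or recuts of outside tissue is required for histologic review prior to enrollment as part of the screening process".
- Footnote 4 to the section 8 schedule: "Central review of pathology at Duke is required at baseline".
- The schedule itself marks central histology review in the screening column.
- The synopsis design paragraph says baseline tissue is assessed at Duke for eligibility.

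Section 8.2.3 allows enrolment only once all pre-treatment screening evaluations are complete, so it matters whether central review is one of them.

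**Analysis.** Section 5.10 puts every enrolled man who receives at least one dose into the intention-to-treat analysis of the primary endpoint. Section 8.11.4 limits the main response-rate analysis to treated men who meet the eligibility criteria and bases conclusions on all eligible subjects. Section 11.5.3 says "Ineligible subjects and subjects who cancel registration before receiving any therapy will not be included in the analyses".

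**The concern.** Under section 7.1 a man can be enrolled and dosed on a local read, with the central read following weeks later. Under 8.9.3 he could not be enrolled until slides had been supplied for review. Once stage 2 adds sites, different sites could follow different sections and admit different men.

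The more serious consequence is for the primary endpoint. If a late central read calls a treated man's eligibility into question, the protocol does not settle whether he counts. That choice could be made when his scans are already known, with no blinding and no comparator arm. With thresholds this low, the choice can decide the trial.

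**Working it through.** **1. The design as stated.** Inputs from section 11.1: the trial is planned "to reject the null hypothesis of response rate of 5% when the true response rate was 20"%; "Type 1 error rate (one-sided) is 0.05"; 18 men in stage 1, stopping at one or fewer responses; 26 more for a total of 44; success at five or more responses; stated power 88%; stated probability of early termination under the null 0.77.

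With X1 ~ Bin(18, p) and X2 ~ Bin(26, p),

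P(success) = sum over x1 ≥ 2 of P(X1 = x1) × P(X2 ≥ 5 − x1).

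At p = 0.20:
- x1 = 2: 0.1723 × 0.9159 = 0.1578
- x1 = 3: 0.2297 × 0.9773 = 0.2245
- x1 = 4: 0.2153 × 0.9970 = 0.2147
- x1 ≥ 5: 0.2836

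The sum is 0.8806. At p = 0.05 the same formula gives a type I error of 0.0495, and P(X1 ≤ 1) = 0.7735. All three stated figures reproduce.

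**2. What one man can do.**
- Stage 1: 2 responses in 18 continues. If one of the two responders is removed, 1 in 17 falls under the stopping rule.
- Final: 5 responses in 44 (11.4%) is declared promising. If one responder is removed, 4 in 43 (9.3%) is not.

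Removing a non-responder leaves the counts unchanged but raises the reported rate: 5/43 = 11.6%.

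**3. The analysis rules side by side, for a dosed man judged ineligible afterwards.**

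| Section | Does he count in the primary response rate? |
|---|---|
| 5.10 | Yes: enrolled and dosed |
| 8.11.4 | No: only men meeting eligibility criteria |
| 11.5.3, read literally | No: ineligible subjects are left out |

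Section 11.5.3 is ambiguous, because its phrase about not having received therapy could qualify both groups it names. Section 8.11.4 has no such ambiguity, so the conflict with 5.10 remains either way.

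**4. Power, if men were dropped from stage 1 and not replaced.** Assumptions: the same cut-offs (continue at 2 or more, succeed at 5 or more), the total still brought to 44, and a true rate of 20%. The number dropped is assumed, since the documents give no rate of local–central disagreement.

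| Stage-1 men left | Chance of stopping after stage 1 | Power |
|---|---|---|
| 18 (as designed) | 9.9% | 88.1% |
| 17 | 11.8% | 86.3% |
| 16 | 14.1% | 84.2% |
| 15 | 16.7% | 81.7% |
| 14 | 19.8% | 78.8% |

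The loss comes from stopping more often after stage 1. If instead stage 1 stays at 18, only 44 men are treated in all, and the losses fall in stage 2, then 1, 2 or 4 dropped gives 87.7%, 87.3% or 86.2%. If 5 of 49 are dropped with 18 evaluable kept in stage 1, 44 remain and power is 88.1%.

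**The case against.** A reader might infer that a treated man found ineligible on central review is dropped and that the 88% power is therefore eroded. The documents do not support that, for five reasons.

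- Section 5.10 says the opposite about who is analysed. If it governs, nobody is dropped and this mechanism costs no power.
- A discordant central read does not in itself make a man ineligible. Section 7.1 gives the eligibility decision to local review. A change among small cell, intermediate atypical and mixed histology stays within Criterion 1, and a man re-read as pure adenocarcinoma may still meet Criterion 2.
- Stage 1 is at Duke only (section 5.1), and the central reviewer is also at Duke. Divergence between sites cannot arise there, although an outside report could still serve as the local read.
- Section 11.1 raises 44 to 49 for a 10% unevaluable rate. Men never dosed are replaced (8.8.3), and men unassessed because of rapid progression or toxicity count as non-responders (8.10.6). The allowance is therefore largely free to absorb about five ineligible men.
- No section says the stage-1 decision would be taken on fewer than 18 evaluable men.

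All of this stands as a limit on the power argument. It leaves two things untouched: the contradictory entry rules, and the lack of a single primary denominator. The 18 in stage 1 also carries no stated inflation or top-up rule.

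**Conclusion.** The point holds as two linked contradictions: when central pathology review must occur relative to entry, and whether a dosed man later judged ineligible counts in the primary response rate. Together they leave the primary denominator open to change after response is known. One responder kept or removed can reverse the decision at 2 of 18 or at 5 of 44.

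Lost power is not an established consequence. It is zero if 5.10 governs, or if 18 evaluable men in stage 1 and 44 overall are kept. The fall to between 86.3% and 78.8% requires three things: that the exclusion rule is applied, that the losses fall in stage 1, and that stage 1 is not topped up. The one to four men dropped are an assumed range. The case for change rests on bias in the denominator and on consistent entry, and it should be made before stage 2 brings in further sites.

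**What to change.** 1. **One entry rule.** Reconcile the synopsis design paragraph, the schedule row, footnote 4 and section 8.9.3 objective 3 with inclusion criteria 1 and 3, so that local review decides eligibility throughout.
2. **One primary denominator.** Amend 8.11.4 and 11.5.3 to match 5.10, so that every dosed man stays in the primary response rate whatever the central read shows.
3. **A defined role for central review.** State that it assigns histologic subtype for reporting, and add a sensitivity response rate in centrally confirmed men.
4. **Counting.** State that the 18 and the 44 are counted on this same set, and which cut-offs apply if the analysed number differs. If all 49 were dosed and analysed with the success rule left at five, type I error would be 0.065 instead of 0.0495.

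The cost is wording in a handful of places and one extra line of analysis. The downside is small: a few centrally discordant men stay in the primary denominator, and the sensitivity analysis shows how much they matter.
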